### 10.5.3. Definition of Device Deficiency

Device Deficiency Definition

• A device deficiency is an inadequacy of a medical device with respect to its identity, quality, durability, reliability, safety, or performance. Device deficiencies include malfunctions, use errors, and inadequate labeling.

#### 10.5.4. Recording/Reporting and Follow-up of AEs and/or SAEs and Device Deficiencies

AE and SAE, and Device Deficiency Recording

When an AE/SAE/device deficiency occurs, it is the responsibility of the investigator to review all documentation (eg, hospital progress notes, laboratory reports, and diagnostic reports) related to the event.

The investigator will then record all relevant AE/SAE/device deficiency information in the participant's medical records, in accordance with the investigator's normal clinical practice and on the appropriate form of the CRF.

It is not acceptable for the investigator to send photocopies of the participant's medical records to Pfizer Safety in lieu of following the reporting process described in the IP Manual and completing the Medical Device Complaint CRF.

There may be instances when copies of medical records for certain cases are requested by Pfizer Safety. In this case, all participant identifiers, with the exception of the participant number, will be redacted on the copies of the medical records before submission to Pfizer Safety.

The investigator will attempt to establish a diagnosis of the event based on signs, symptoms, and/or other clinical information. Whenever possible, the diagnosis (not the individual signs/symptoms) will be documented as the AE/SAE.

For device deficiencies, it is very important that the investigator describes any corrective or remedial actions taken to prevent recurrence of the incident.

A remedial action is any action other than routine maintenance or servicing of a medical device where such action is necessary to prevent recurrence of a device deficiency. This includes any amendment to the device design to prevent recurrence.

Assessment of Intensity

The investigator will make an assessment of intensity for each AE/SAE/device deficiency reported during the study and assign it to 1 of the following categories:
 

Mild: An event that is easily tolerated by the participant, causing minimal discomfort and not interfering with everyday activities.

Moderate: An event that causes sufficient discomfort and interferes with normal everyday activities.

Severe: An event that prevents normal everyday activities. An AE that is assessed as severe should not be confused with an SAE. Severe is a category utilized for rating the intensity of an event; and both AEs and SAEs can be assessed as severe.

- An event is defined as "serious" when it meets at least 1 of the predefined outcomes as described in the definition of an SAE, NOT when it is rated as severe.

### Assessment of Causality

- The investigator is obligated to assess the relationship between study intervention and each occurrence of each AE/SAE/device deficiency.
- A "reasonable possibility" of a relationship conveys that there are facts, evidence, and/or arguments to suggest a causal relationship, rather than a relationship cannot be ruled out.
- The investigator will use clinical judgment to determine the relationship.
- Alternative causes, such as underlying disease(s), concomitant therapy, and other risk factors, as well as the temporal relationship of the event to study intervention administration will be considered and investigated.
- The investigator will also consult the IB and/or product information, for marketed products, in his/her assessment.
- For each AE/SAE/device deficiency, the investigator must document in the medical notes that he/she has reviewed the AE/SAE/device deficiency and has provided an assessment of causality.
- There may be situations in which an SAE has occurred and the investigator has minimal information to include in the initial report to the sponsor. However, it is very important that the investigator always make an assessment of causality for every event before the initial transmission of the SAE data to the sponsor.
- The investigator may change his/her opinion of causality in light of follow-up information and send an SAE follow-up report with the updated causality assessment.
- The causality assessment is one of the criteria used when determining regulatory reporting requirements.

### Follow-up of AE/SAE/Device Deficiency

- The investigator is obligated to perform or arrange for the conduct of supplemental measurements and/or evaluations as medically indicated or as requested by the sponsor to elucidate the nature and/or causality of the AE/SAE/device deficiency as fully as possible. This may include additional laboratory tests or investigations, histopathological examinations, or consultation with other healthcare providers.

- If a participant dies during participation in the study or during a recognized follow-up period, the investigator will provide Pfizer Safety with a copy of any postmortem findings including histopathology.
- New or updated information will be recorded in the originally completed CRF.
- The investigator will submit any updated SAE data to the sponsor within 24 hours of receipt of the information.

#### 10.5.5. Reporting of SAEs

##### SAE Reporting to Pfizer Safety via an Electronic Data Collection Tool

- The primary mechanism for reporting an SAE to Pfizer Safety will be the electronic data collection tool.
- If the electronic system is unavailable, then the site will use the paper SAE data collection tool (see next section) in order to report the event within 24 hours.
- The site will enter the SAE data into the electronic system as soon as the data become available.
- After the study is completed at a given site, the electronic data collection tool will be taken off-line to prevent the entry of new data or changes to existing data.
- If a site receives a report of a new SAE from a study participant or receives updated data on a previously reported SAE after the electronic data collection tool has been taken off-line, then the site can report this information on a paper SAE form (see next section) or to Pfizer Safety by telephone.

##### SAE Reporting to Pfizer Safety via Vaccine SAE Reporting Form

- Facsimile transmission of the Vaccine SAE Reporting Form is the preferred method to transmit this information to Pfizer Safety.
- In circumstances when the facsimile is not working, notification by telephone is acceptable with a copy of the Vaccine SAE Reporting Form sent by overnight mail or courier service.
- Initial notification via telephone does not replace the need for the investigator to complete and sign the Vaccine SAE Reporting Form pages within the designated reporting time frames.

#### 10.5.6. Reporting of SADEs

##### SADE Reporting to Pfizer Safety

NOTE: There are additional reporting obligations for medical device incidents that are potentially related to SAEs that must fulfill the legal responsibility to notify appropriate regulatory authorities and other entities about certain safety information relating to medical devices being used in clinical studies.

- Any device deficiency that is associated with an SAE must be reported to the sponsor within 24 hours after the investigator determines that the event meets the definition of a device deficiency.
- The sponsor shall review all device deficiencies and determine and document in writing whether they could have led to an SAE. These shall be reported to the regulatory authorities and IRBs/ECs as required by national regulations.

## **10.6. Appendix 6: Alternative Measures During Public Emergencies**

The alternative study measures described in this section are to be followed during public emergencies, including the COVID-19 pandemic. This appendix applies for the duration of the COVID-19 pandemic and will become effective for other public emergencies only upon written notification from Pfizer.

Use of these alternative study measures are expected to cease upon the return of business as usual (including the lifting of any quarantines and travel bans/advisories).

### **10.6.1. Telehealth Visits**

In the event that in-clinic study visits cannot be conducted, every effort should be made to follow up on the safety of study participants at scheduled visits per the [SoA](#) or unscheduled visits. Telehealth visits may be used to continue to assess participant safety and collect data points. Telehealth includes the exchange of healthcare information and services via telecommunication technologies (eg, audio, video, videoconferencing software) remotely, allowing the participant and the investigator to communicate on aspects of clinical care, including medical advice, reminders, education, and safety monitoring. The following assessments must be performed during a telehealth visit:

- Review and record any AEs and SAEs since the last contact. Refer to [Section 8.3](#).
- Review and record any new concomitant medications used to treat an AE since the last contact. Refer to [Section 6.5](#).
- Confirm that the participant is adhering to the contraception method(s) required in the protocol. Refer to [Appendix 3](#).

Study participants must be reminded to promptly notify site staff about any change in their health status.

### **10.6.2. Home Health Visits**

A home health care service may be utilized to facilitate scheduled visits per the SoA. Home health visits include a healthcare provider conducting an in-person study visit at the participant's location, rather than an in-person study visit at the site. The following may be performed during a home health visit:

- Ensure that the participant continues to be eligible for the study, and continues to comply with contraception requirements as detailed in [Section 5.3.1](#).
- Ensure that the participant continues to meet none of the withdrawal criteria as described in [Section 7.2](#).
- If previously provided to the participant's parent(s)/legal guardian, collect the provisioned e-diary device.

- Review the participant's e-diary data since the previous visit and follow up on any ongoing reactogenicity or use of antipyretic medication.
- Complete the Study Visit/Telephone Contact AE Checklist to:
  - Inquire whether the participant had any NDCMCs since the last visit. Inquire whether the participant had any of the following related to an AE since the last visit: hospitalizations, visits to other medical facilities, medication use, or missed days of school or work. Please refer to the ISF for additional details.
  - Inquire about neuroinflammatory and autoimmune conditions, such as transverse myelitis, uveitis, optic neuritis, and multiple sclerosis. Please refer to the ISF for additional details.
- Record AEs as described in the AE reporting requirements section ([Section 8.3](#)) and the [SoA](#).
- Report any SAEs to the sponsor as defined in [Section 8.3](#).
- Review AEs that were ongoing since the previous visit and record their end dates or confirm that they are still continuing.
- Record nonstudy vaccinations as described in the Concomitant Therapy section ([Section 6.5](#)).
- Record any blood transfusion (eg, whole blood, packed cells) received by the participant as described in the Concomitant Therapy section ([Section 6.5](#)).
- Record concomitant medications used to treat AEs as described in the Concomitant Therapy section ([Section 6.5](#)).
- Provide the parent(s)/legal guardian or the participant with a memory aid. Instruct the participant to use the memory aid between visits (Visits 2 and 3, or Visits 4 and 5, as applicable) to remind him or her to review any significant illnesses, hospitalizations, NDCMCs, or visits to a medical facility with study site personnel. The memory aid is not a diary for the collection of reactogenicity. Please refer to the ISF and [Section 8.2](#) for additional details.
- Ask the parent(s)/legal guardian or the participant to contact the investigator immediately if any significant illness or hospitalization occurs.
- Schedule an appointment for the next study visit and confirm that it is scheduled within the time window per protocol.
- Complete the source documents.

- Complete the CRFs.

#### **10.6.3. Adverse Events and Serious Adverse Events**

If a participant has COVID-19 during the study, this should be reported as an AE or SAE and appropriate medical intervention provided. Study intervention should continue unless the investigator/treating physician is concerned about the safety of the participant, in which case temporary or permanent discontinuation may be required.

It is recommended that the investigator discuss temporary or permanent discontinuation of study intervention with the study medical monitor.

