### Protocol Amendment Summary of Changes Table

Document History		
Document	Version Date	Summary and Rationale for Changes
Original protocol	22 January 2021	N/A

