#### 4.1.1. Approximate Duration of Participation for Each Participant

The duration of study participation for each participant will be approximately 12 months, including a telephone contact 6 months after the last vaccination.

The study duration will be approximately 3 years. The sponsor may decide to close recruitment if enrollment of 50 participants becomes challenging after 2 years of active enrollment.

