### 9.2. Sample Size Determination

The study sample size is not based on any hypothesis-testing criteria. The study aims to enroll up to 50 participants to allow for sufficient numbers when describing findings with regard to this particular population.

The probability of observing at least 1 occurrence of any AE for true event percentages between 1.0% and 5.0%, when Trumenba is administered to 50 participants, is displayed in Table 6.

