### 9.4.1. Historical Age-Matched Healthy Controls

Historical data from age-matched healthy participants from Study B1971057, a pivotal Phase 3 MnB study that has previously completed the primary analysis, will be used as a reference for safety and immunogenicity of Trumenba. Healthy adolescents and young adults (10 to <26 years of age) from B1971057 will be randomly selected and a historical age-matched healthy control group will be used to provide context and assist with the interpretation of the immunogenicity and safety data for the immunocompromised participants. The safety and immunogenicity data will be reported separately for the immunocompromised and healthy control participants. The selection of the participants for the historical age-matched controls is based on 1 previously completed Phase 3 MnB study, B1971057 (Stage 1). Study B1971057 followed the same 0- and 6-month dosing schedule and used the same methodology for assessment of immunogenicity and safety as in this study. Healthy adolescents and young adults (10 to <26 years of age) were enrolled in B1971057 and the immunopersistence stage of the study (Stage 2) is ongoing. The same age distribution will be ensured for both the healthy controls and the immunocompromised participants by randomly selecting age-matched healthy participants from Study B1971057

who were randomized to Trumenba. For immunocompromised participants 10 to <26 years of age in this study, age-matched control participants will be randomly selected from Study B1971057. For immunocompromised participants older than 25 years of age in this study, the controls will be randomly selected from participants 25 years of age from Study B1971057. No participants will be randomly selected as control more than once. For Study B1971057, only participants randomized to Group 2 or Group 4 (Trumenba groups) will be eligible to be selected as healthy controls. Further details will be available in the SAP.

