6.1.2.5. Serious Adverse Events and Medically Attended Adverse Events

- Summary: The percentages of participants with at least 1 SAE and at least 1 MAE occurring during the 30 days after each vaccination, during the 30 days after any vaccination, during the vaccination phase, during the follow-up phase, and from Vaccination 1 through 6 months after Vaccination 2 ([Section 2.1](#)). The descriptive analyses will be displayed separately for immunocompromised participants, and for age- and sex-matched healthy controls from historical data.
- Analysis sets: Safety populations for immunocompromised participants, and historical data of the age- and sex-matched healthy participants. Refer to [Section 4](#) for visit-specific populations.
- Intercurrent event(s): Participants will be analyzed according to the vaccine they actually received. Missing AE dates will be handled according to the Pfizer safety rules.
- Analysis methodology: Descriptive summary statistics including associated Clopper-Pearson 95% CIs.
- Reporting results: For each participant group, the numbers and percentages of participants with SAEs and MAEs for the analysis intervals defined in [Table 10](#) will be summarized. The numerator (n) and the denominator (N) used in the percentage calculation, the percentage (%), and the corresponding 2-sided 95% CI will be presented for any event.

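### COVID-19 counts as an AE or SAE in this trial and no planned any-event row excludes it, so AE, MAE and SAE percentages may differ by era from the historical controls

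*Protocol*

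**What the plan says.** **COVID-19 in this trial.** Protocol Section 10.6.3 says "If a participant has COVID-19 during the study, this should be reported as an AE or SAE and appropriate medical intervention provided". The parent appendix (Section 10.6) says of itself "This appendix applies for the duration of the COVID-19 pandemic". The protocol is dated "22 January 2021", and Section 4.1.1 adds "The study duration will be approximately 3 years".

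**The controls.** Protocol Section 9.4.1 takes them from B1971057, described as "a pivotal Phase 3 MnB study that has previously completed the primary analysis". It names Stage 1 as the completed part and says that Stage 2 is still running. SAP Section 2.2.1 reports the controls for the same endpoints, intervals and populations as the trial group, and gives their purpose as context and help in interpreting the immunogenicity and safety data.

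**The planned rows.**
- AEs (SAP Section 6.1.2.4): any-event, system organ class and preferred-term rows are optional for the percentages with confidence intervals.
- SAEs and MAEs (SAP Section 6.1.2.5): only the overall row is specified: "the corresponding 2-sided 95% CI will be presented for any event".
- Related events (SAP Section 6.6.1.1): AEs and SAEs judged related by the investigator are summarized separately. MAEs are not named there.

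The readable SAP text does not mention COVID-19.

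**The concern.** The controls are there so that a reader can judge whether the safety profile in asplenic and complement-deficient participants looks unusual. An illness that circulates in one data-collection period and little or not at all in the other raises the any-event percentages in one column only. The direction is known: it makes the immunocompromised group look worse. A reader of two adjacent any-event percentages could take the difference for an effect of immune status, and the planned MAE table would give no way to check.

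No hypothesis is tested, so no error rate is at stake. What is at stake is the reading of the side-by-side safety percentages.

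**Working it through.** **1. The plan's own figures.** No figure in the documents concerns COVID-19. The nearest are Tables 6 and 7 of Protocol Section 9.2, for 50 participants ("The study aims to enroll up to 50 participants").
- Table 6, 1-(1-p)^50 at p = 1.0%, 1.5%, 2.0%, 3.2%, 5.0%: 0.395, 0.530, 0.636, 0.803, 0.923. Stated: 0.39, 0.53, 0.64, 0.80, 0.92.
- Table 7, Clopper-Pearson widths at 0.5 to 0.9: 0.2895, 0.2841, 0.2675, 0.2369, 0.1849. Stated: 0.289, 0.284, 0.267, 0.237, 0.185.

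Both tables reproduce and are not in dispute. By the same formula, if 5% of participants had COVID-19, the chance of at least one case among 50 would be 0.92.

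**2. When the controls were followed.** No dates are given, so this is an inference. Assume that completion of Stage 1 includes the Visit 5 call and that this protocol's visit windows also applied in B1971057. The shortest path from first dose to Visit 5 is 173 + 168 = 341 days. Counting back from 22 January 2021 gives 16 February 2020 as the latest first dose. That bounds the overlap but does not remove it: a participant dosed near that date would have been followed through most of 2020. The primary analysis was already complete at the protocol date, and Protocol Section 2.2.1 quotes its immunogenicity results, so earlier follow-up is probable for most controls.

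**3. Shift in an any-event percentage.** Let p be the proportion with a non-COVID event and c the proportion with a COVID-19 event in the same interval. Assume that the two are independent and that controls have no COVID-19. The reported rate is p + (1-p) x c, so the shift is (1-p) x c. Neither p nor c is in the documents.

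| p | c = 5% | c = 10% | c = 20% | c = 30% |
|---|---|---|---|---|
| 10% | 4.5 | 9.0 | 18.0 | 27.0 |
| 20% | 4.0 | 8.0 | 16.0 | 24.0 |
| 40% | 3.0 | 6.0 | 12.0 | 18.0 |
| 50% | 2.5 | 5.0 | 10.0 | 15.0 |

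(Percentage points.) The exact 95% interval at N = 50 is 18.5 points wide at 10% observed, 23.7 at 20% and 28.4 at 40%. The left of the table lies well inside those widths; the right is comparable with them.

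**4. The interval matters.** Read the top case, 30%, as a 12-month figure with constant hazard. For d days, c = 1 - 0.7^(d/365).
- 30-day window (vaccination date to date + 30, inclusive, d = 31): c = 3.0%. Shift 0.5 x 3.0 = 1.5 points at p = 50%, and 0.9 x 3.0 = 2.7 at p = 10%.
- Vaccination phase, d = 173 + 28 = 201 to 194 + 42 = 236: c = 17.8% to 20.6%. Shift 8.9 to 10.3 points at p = 50%, and 16.0 to 18.5 at p = 10%.

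For MAEs, c counts only nonserious cases seen at a medical facility, so it is at most the overall figure.

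**5. SAEs.** With an assumed 2% background and a COVID-19 SAE rate of 0.5% to 2%, the reported rate is 0.02 + 0.98 x c = 2.5% to 4.0%, a shift of about 0.5 to 2 points. The chance of at least one such SAE among 50 is 0.22 to 0.64.

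**6. What the planned summaries can separate.**

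| Event type | Any-event row excluding COVID-19 | Preferred-term rows | Related-event summary |
|---|---|---|---|
| AE | none | optional | required |
| SAE | none | not specified in 6.1.2.5 | required |
| MAE | none | not specified | none |

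A preferred-term row would show how many participants had COVID-19. It would not show how many had at least one other event, because one participant can have both.

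**The case against.** The case against acting has several parts.

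- *The era gap is not documented.* Stage 1 dates, trial enrollment dates and COVID-19 rates are all missing. A reader might infer that COVID-19 is absent from the controls, or that the percentages do differ by era. The documents support only that they may.
- *The plan is not silent.* A reader might infer that nothing planned separates COVID-19. That goes too far: COVID-19 judged unrelated drops out of the required related-AE and related-SAE summaries, and optional preferred-term rows could display it. Table shells and listings are prepared separately (SAP Section 2) and may show more. This stands in part. The related summaries, however, remove every unrelated event, depend on investigator attribution (open-label here, observer-blinded in B1971057), and do not cover MAEs.
- *The large figures are stacked assumptions.* A reader might take 15 or 27 points as the expected distortion. Those need 30% incidence within the interval and no COVID-19 in controls, and the 27-point figure for MAEs also needs every case medically attended. In a 30-day window the any-AE shift is near 1.5 points even in that top case. This stands.
- *The study is descriptive and the groups already differ.* Patients are set beside healthy volunteers, and those older than 25 are matched to participants about that age. This limits the consequence but does not make a removable one-directional difference worth keeping.
- *The reporting rule is ordinary.* A new illness is an AE under Protocol Section 10.2.1 anyway. Agreed: the rule is not at fault, only the lack of a summary that allows for it.
- *The remedy is partial.* If other infections fell during the pandemic, removing COVID-19 alone could tilt the comparison the other way. This stands and needs a footnote.

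**Conclusion.** The point holds as a cheap reporting improvement, not as an error in the analysis. COVID-19 enters the trial's AE, MAE and SAE counts, probably enters the control counts much less, and is excluded from none of the any-event rows. The gap is clearest for MAEs and for the longer intervals.

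The size cannot be derived from the documents. On assumed rates the any-event shift runs from 2.5 to 27 points across the table above, with the upper end an extreme case; it is small in 30-day windows and probably small for SAEs. All of this assumes independence and no COVID-19 in controls. Any Stage 1 follow-up that fell within the pandemic makes the shift smaller.

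**What to change.** In SAP Sections 6.1.2.4 and 6.1.2.5, keep every planned table and add, for both groups:

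1. the number and percentage of participants with a COVID-19 preferred term;
2. a row labelled supplementary giving participants with at least one AE, MAE or SAE excluding COVID-19 preferred terms. It matters most for the vaccination phase (AEs, MAEs, SAEs) and for the follow-up and full-study intervals (MAEs and SAEs, since SAP Table 11 does not report all AEs there).

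Add a footnote giving the calendar period of Stage 1 safety collection and saying that the row does not correct for other pandemic-era changes, such as fewer other infections. Fix the list of preferred terms before database release, because the sponsor may look at the data during this open-label study and a list chosen later could be data-driven.

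The cost is SAP wording, two rows per table and a footnote. Events are already MedDRA-coded and the Stage 1 analysis data sets are already to be used, so no new data are needed. Section 6.1.2.5 needs an edit in any case: it points to Table 10, the reactogenicity intervals, where the SAE and MAE intervals are in Table 11. The downside is that the supplementary row is a partial correction and must not replace the planned percentages.
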